1 LIST OF ABBREVIATIONS

Abbreviation	Definition
ACEI	Angiotensin-Converting Enzyme Inhibitor
AE	Adverse Event
ARB	Angiotensin Receptor Blocker
ARNI	Angiotensin Receptor Neprilysin Inhibitor
CRF	Case Report Form
DSMB	Data Safety Monitoring Board
EF	Ejection Fraction
eGFR	Estimated Glomerular Filtration Rate
GFR	Glomerular Filtration Rate
HF	Heart Failure
HFpEF	Heart Failure with Preserved Ejection Fraction
HFrEF	Heart Failure with Reduced Ejection Fraction
ITT	Intention To Treat
IRB	Institutional Review Board
LV	Left Ventricular
LVAD	Left Ventricular Assist Device
LVEF	Left Ventricular Ejection Fraction
mmHG	Millimeters of mercury
mmol/L	Millimole per liter
MDRD	Modification of Diet in Renal Disease
NT-proBNP	N-terminal pro-B-type natriuretic peptide
PO	“Per os,” or by mouth
PPI	Patient Package Insert
SAE	Serious Adverse Event
SBP	Systolic Blood Pressure
sST2	Soluble ST2

3 EXECUTIVE SUMMARY

Title	Protecting with ARNI Against Cardiac Consequences of Coronavirus Disease 2019 (PARACOR-19)
Indication	To decrease risk of cardiac injury and abnormalities in cardiac structure and function following COVID-19 infection
Location	Duke University Hospital
Brief Rationale	
Although many patients presenting with Coronavirus Disease 2019 (COVID-19) face high-risk of death, the vast majority of patients recover from the acute infection, either in the hospital or at home. Nonetheless, despite clinical improvement or resolution of symptoms, accumulating evidence supports significant potential for longer-term and insidious cardiac involvement. Moreover, within the heart, the virus appears to localize to interstitial cells and the extracellular matrix, with relative sparing of the myocytes themselves. These data, combined with others noting high levels of inflammation with COVID-19, suggest that the virus may increase propensity for downstream cardiac fibrosis and dysfunction. These collective data raise significant concerns that cardiomyopathy, heart failure, or other cardiovascular complications will evolve as the natural history of COVID-19 for many patients who recover from acute infection.
 
Pre-clinical and clinical data across multiple cardiometabolic conditions suggest that sacubitril/valsartan may be particularly well-suited to prevent adverse cardiac remodeling and new-onset HF following COVID-19 infection. Renin-angiotensin-aldosterone system (RAAS) inhibition has been postulated to have a cardio-protective role in COVID-19, but there is biologic plausibility that a dual compound with a neprilysin inhibitor would better prevent cardiac injury and dysfunction. In this context, the goal of the PARACOR-19 trial is to generate further evidence regarding the effects of sacubitril/valsartan on markers of cardiac injury, structure, and function among patients who have recovered from acute COVID-19 infection.
 
Hypothesis: Among patients with cardiovascular risk factors and 4-16 weeks from prior COVID-19 infection, sacubitril/valsartan will reduce levels of high-sensitivity troponin T and/or soluble ST2 (sST2), compared with placebo.

Study Design	The PARACOR-19 trial will be an investigator-initiated, single center, double-blind trial of patients who have recovered from acute COVID-19

	infection. There will be 1:1 randomization to sacubitril/valsartan or placebo. Approximately 50 participants will be randomized into the study. A subset of approximately 30 patients will be enrolled in the cardiac magnetic resonance (CMR) sub-study.
Treatment	Sacubitril/valsartan versus placebo
Primary Objective and Endpoint	
 1. Change from baseline in high-sensitivity troponin T 2. Change from baseline in sST2
Exploratory Objectives and Endpoints	
 1. Change from baseline in high-sensitivity C-reactive peptide 2. Change from baseline in PINP 3. Change from baseline in Galectin-3 4. Change from baseline in NT-proBNP 5. Change from baseline in GDF-15 6. Change from baseline in IL-6 7. Change from baseline in CITP 8. Change from baseline in CMR measures (LVEF, LVEDVi, LVESVi, Native T1, Native T2) 9. Change from baseline in focal fibrosis by delayed-enhancement 10. Change from baseline in focal fibrosis as percentage of LV myocardial mass 11. Change from baseline in health related quality of life, as measured by EQ-5D utility score and EQ-5D visual analog scale

4 OBJECTIVES

4.1 Primary Objectives

To determine the effect of sacubitril/valsartan versus placebo over 12 weeks on biomarkers of cardiac injury and fibrosis, as reflected in changes in high-sensitivity troponin T and sST2.

Hypothesis: Among patients with cardiovascular risk factors and 4-16 weeks from prior COVID-19 infection, sacubitril/valsartan will reduce levels of high-sensitivity troponin T and/or soluble ST2 (sST2), compared with placebo.

4.2 Exploratory Objectives

To determine the effect of sacubitril/valsartan versus placebo over 12 weeks on cardiac biomarkers and measures of cardiac dysfunction and fibrosis on cardiac magnetic resonance imaging, as reflected by the following exploratory endpoints:

1. Change from baseline in high-sensitivity C-reactive peptide
2. Change from baseline in PINP
3. Change from baseline in Galectin-3
4. Change from baseline in NT-proBNP
5. Change from baseline in GDF-15
6. Change from baseline in IL-6
7. Change from baseline in CITP
8. Change from baseline in cardiac MRI (CMR) measures (LVEF, LVEDVi, LVESVi, Native T1, Native T2)
9. Change from baseline in focal fibrosis by delayed-enhancement
10. Change from baseline in focal fibrosis as percentage of LV myocardial mass
11. Change from baseline in health related quality of life, as measured by EQ-5D utility score and EQ-5D visual analog scale

5 BACKGROUND AND STUDY RATIONALE

Although many patients presenting with Coronavirus Disease 2019 (COVID-19) face high-risk of death, the vast majority of patients recover from the acute infection, either in the hospital or at home. Nonetheless, despite clinical improvement or resolution of symptoms, accumulating evidence supports significant potential for longer-term and insidious cardiac involvement. For example, in a recent study of patients seen a mean 71 days after COVID-19 diagnosis, 76% had detectable high-sensitivity troponin, 78% had demonstrable cardiac involvement on cardiac magnetic resonance (CMR) imaging, and 60% had evidence of cardiac inflammation by abnormal T1 and T2 imaging.¹ Two-thirds of these patients recovered at home and there were no meaningful differences in troponin or CMR measures between patients who did and did not require hospitalization, suggesting that ongoing cardiac involvement may be common even

among those with a mild acute presentation.¹ Likewise, in an autopsy study of patients with COVID-19 pneumonia as the clinical cause of death, 62% of patients had virus present in the heart, despite not meeting clinical or histologic criteria for acute myocarditis.² Viral load was high and evidence of active viral replication was seen in most cases.² Notably, the virus appeared to localize to interstitial cells and the extracellular matrix of the heart, with relative sparing of the myocytes themselves.³ These data, combined with others noting high levels of inflammation with COVID-19, suggest that the virus may increase propensity for downstream cardiac fibrosis and dysfunction. These collective data raise significant concerns that cardiomyopathy and heart failure will evolve as the natural history of COVID-19 for many patients who recover from acute infection.⁴

Pre-clinical and clinical data across multiple cardiometabolic conditions suggest that sacubitril/valsartan may be particularly well-suited to prevent adverse cardiac remodeling and new-onset HF following COVID-19 infection. Renin-angiotensin-aldosterone system (RAAS) inhibition has been postulated to have a cardio-protective role in COVID-19, but there is strong biologic plausibility that a dual compound with a neprilysin inhibitor would better prevent cardiac injury and dysfunction.⁵ Across cardio-renal disease states, compared with ACEI/ARB therapy, sacubitril/valsartan offers superior cardio-protection for reducing clinical events and biomarkers of cardiac injury/ wall stress (e.g., troponin, natriuretic peptides), and these incremental benefits emerge quickly within a few weeks.⁶⁻¹¹ Likewise, compared with ACEI/ARB, sacubitril/valsartan lowers levels of pro-inflammatory cytokines and other inflammatory biomarkers.¹²⁻¹⁴ Most recently, among patients with preserved ejection fraction, sacubitril/valsartan was shown to favorably alter biomarkers of cardiac extracellular matrix and collagen regulation compared with valsartan, adding further support for an anti-fibrotic mechanism well-suited to combat the propensity of COVID-19 for the cardiac interstitium.¹⁵

In this context, the goal of the PARACOR-19 trial is to generate further evidence regarding the effects of sacubitril/valsartan on markers of cardiac injury, structure, and function among patients who have recovered from acute COVID-19 infection.

6 STUDY DESIGN

6.1 Screening and Randomization (Study Visit 1)

Willing participants deemed likely to meet eligibility criteria will be consented. Participants will have an initial screening evaluation, including laboratory tests, at which time preliminary subject eligibility will be confirmed. Patients will also complete EuroQOL-5D (EQ-5D) surveys in order to be eligible. Participants consenting for and meeting entry criteria for the CMR substudy will undergo a CMR examination.

Patients confirmed to meet study eligibility criteria will be randomized 1:1 in double-blind fashion to sacubitril/valsartan twice daily versus matching placebo twice daily. The starting dose of study drug will be dictated by systolic blood pressure. If systolic blood pressure is 100-120 mmHg at randomization, participants will receive sacubitril/valsartan 24/26 mg twice daily or

matching placebo. If systolic blood pressure >120 mmHg at randomization, participants will receive sacubitril/valsartan 49/51 mg twice daily or matching placebo. At time of randomization, patients will also have serum biomarkers collected for central and local laboratory analysis.

6.2 Dose Titration and Safety Visit

Patients will return between 7 and 21 days post-randomization for **Study Visit 2**. At this visit, tolerability and adherence to study medication will be assessed, renal function and potassium levels will be checked via local labs, and patients will have the dose of medication titrated based on systolic blood pressure and clinician assessment regarding presence of symptomatic hypotension.

If systolic blood pressure >100 mmHg and no symptomatic hypotension or deemed medication-related adverse effects, dose of study medication will be increased to the next highest dose of sacubitril/valsartan or matching placebo (i.e., patients originally receiving sacubitril/valsartan 24/26 mg twice daily will be increased to sacubitril/valsartan 49/51 mg twice daily; patients originally receiving sacubitril/valsartan 49/51 mg twice daily will be increased to sacubitril/valsartan 97/103 mg twice daily). Patients not meeting criteria for dose uptitration will remain on their original dose of study therapy, as tolerated. For patients who are reporting symptomatic hypotension or other possible medication related adverse effects from study drug, the investigator may use their discretion in decreasing the dose of study drug to the next lowest dosing level.

6.3 Final Study Visit

Participants will return for a final study visit between 77 and 91 days (11-13 weeks) for the 12-week visit (**Study Visit 3**). Tolerability and adherence to study medication will be assessed, and renal function and potassium levels will be checked via local labs. Participants will also have serum biomarkers collected for central and local laboratory analysis. Participants who consented for the CMR sub-study will undergo a CMR examination.

7 PATIENT POPULATION

7.1 Study Population

It is anticipated that approximately 50 participants meeting eligibility criteria listed below will be randomized into the study. It is anticipated that 30 of these patients will be included within the CMR substudy. Individuals suitable for this protocol are patients with cardiovascular risk factors and 4-16 weeks from prior COVID-19 infection.

7.2 Inclusion Criteria

1. Patient with a history of laboratory proven-diagnosis of COVID-19 who is 4-16 weeks

from their last positive COVID-19 test

2. Systolic blood pressure ≥ 100 mmHg at screening
3. ≥ 18 years of age
4. Successful collection of baseline serum biomarkers
5. Successful completion of baseline EQ-5D questionnaire
6. Successful completion of baseline CMR study (CMR sub-study only)
7. High-sensitivity troponin at or above the level of detection on screening labs
8. Presence of ≥ 1 of the following:
 - a. Age ≥ 60
 - b. History of atherosclerotic cardiovascular disease (ASCVD), including myocardial infarction, coronary artery disease, ischemic stroke/transient ischemic attack, or peripheral artery disease
 - c. Diabetes mellitus (Type 1 or Type 2)
 - d. Body mass index ≥ 35 kg/m²
 - e. eGFR 30-60 ml/min/1.73m²
 - f. History of atrial fibrillation/flutter

7.3 Exclusion Criteria

1. Fever within the past 96 hours of >100.3 degrees Fahrenheit
2. Actively receiving therapy with an angiotensin-converting enzyme inhibitor (ACEI), angiotensin II receptor blocker (ARB), aliskiren, or sacubitril/valsartan
3. Last known left ventricular ejection fraction of $\leq 40\%$
4. eGFR <30 ml/min/1.73m² on screening labs, including patients on dialysis therapy
5. Serum potassium >5.0 mEq/L on screening labs
6. Prior intolerance, allergy or angioedema to ACEI, ARB, or sacubitril/valsartan
7. Pregnant or breast-feeding
8. In women of childbearing age, unwillingness to use birth control for the duration of the study
9. History of heart transplant or durable left ventricular assist device
10. Currently implanted permanent pacemaker, defibrillator, or other device or condition that would preclude CMR testing (CMR sub-study only)
11. Currently participating in another trial of an investigational medication or device for COVID-19.
12. Any other condition that in the judgment of the investigator would jeopardize the patient's compliance with the study protocol

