8.7 Randomization, Stratification and Blinding

Patients will be consented and enrolled at the first study visit. Eligible patients will be randomized in a 1:1 allocation ratio to one of two treatment groups. Since this is a single center pilot study, randomization will not involve a permuted block design or any stratification.

Blinding of the study, with respect to treatment groups, will be preserved by the use of matching placebo. The investigator may be asked at the end of the trial if they had obtained any

information which may have led to the unblinding of treatment.

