10 VISIT SCHEDULE AND ASSESSMENTS

10.1 Baseline Evaluation, Enrollment and Randomization Visit

A schedule of assessments throughout the study is also provided in Appendix A.

Study Visit 1 (Enrollment and Randomization)

This visit will include the screening and informed consent process followed by a baseline assessment including:

- Demographics and medical history
- Review of medications patient is actively taking, and the doses
- Vital signs, including systolic and diastolic blood pressure, heart rate, height, weight
- EQ-5D quality of life questionnaire
- Residual COVID-19 symptoms
- Local laboratory testing, including the following:
 - Basic metabolic/renal function panel, including sodium, potassium, chloride, CO₂/bicarbonate, blood Urea Nitrogen (BUN), creatinine
 - High-sensitivity troponin

- Central laboratory testing, including the following
 - High-sensitivity troponin T
 - sST2
 - hs-CRP
 - PINP
 - Galectin-3
 - NT-proBNP
 - GDF-15
 - IL-6
 - CITP
- CMR examination, with intravenous gadolinium contrast (CMR sub-study patients only)
- Urine pregnancy test on women of childbearing potential

Patients will be initiated on blinded study medication, as dictated by systolic blood pressure. If systolic blood pressure is 100-120 mmHg at randomization, participants will receive sacubitril/valsartan 24/26 mg twice daily or matching placebo. If systolic blood pressure >120 mmHg at randomization, participants will receive sacubitril/valsartan 49/51 mg twice daily or matching placebo.

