If a subject should stop taking study medication for any reason before completing the 12 weeks of study drug dosing, an attempt should be made to restart the study drug at the last tolerated dose when the subject is stable, per physician discretion. If the treating physician decides to stop study medication and start the patient on an ACEI, then a 36 hour wash-out period is required after the last dose of study drug before starting the ACEI. All subjects will complete all study assessments through study visit 3, regardless of whether they continue to receive the study drug for the full 12 weeks.

Unscheduled Visits:

If the Investigator determines that a participant should be brought to the clinic to be evaluated

for a potential change in study drug dose between scheduled study visits, an “unscheduled visit” should be done. Study drug dose changes will be recorded in the eCRF.

Assessments at this visit include:

- Interim history
- Review of medications patient is actively taking, and the doses
- Vital signs, including systolic and diastolic blood pressure, and heart rate
- Local laboratory testing, including the following:
 - Basic metabolic/renal function panel, including sodium, potassium, chloride, CO₂/bicarbonate, BUN, creatinine
- Adverse event monitoring
- Study medication adherence

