17 APPENDICES

17.1 Appendix A - Schedule of Assessments

Visit number	1 Enrollment/ Randomization	2 Titration Visit (Week 1-2)	3 12 weeks
Time of Visit			
Inclusion/Exclusion criteria	X		
Informed consent	X		
Dispense study medication	X	X	
Demographics, past medical history	X		
Vital signs	X	X	X
Concurrent medications and doses	X	X	X
EQ-5D questionnaire	X		X
Residual COVID Symptoms	X		X
Urine pregnancy test ¹	X	X	X
Local laboratories	X ²	X ³	X ³
Serum biomarkers	X ⁴		X ⁴
Cardiac MRI (30 patients, sub-study patients only)	X		X
Vital status			X
Adverse events, including hospitalizations		X	X
Study medication adherence		X	X

¹ For women of childbearing potential

² hs-TnT, basic metabolic panel (including serum creatinine and serum potassium)

³ Basic metabolic panel (including renal function and serum potassium)

⁴ hs-TnT, sST2, hs-CRP, PINP, Galectin-3, NT-proBNP, GDF-15, IL-6, CITP

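### The entry criteria bar current ACE-inhibitor users but set no minimum time from the last ACE-inhibitor dose to the first dose of study drug

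*Combined protocol and SAP*

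**What the plan says.** Section 7.3, exclusion 2, bars patients "Actively receiving therapy with an angiotensin-converting enzyme inhibitor (ACEI), angiotensin II receptor blocker (ARB), aliskiren, or sacubitril/valsartan". No look-back period is attached. The item just above it does carry one: "Fever within the past 96 hours of >100.3 degrees Fahrenheit".

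Entry and first dosing belong to the same visit. Section 8.7 states "Patients will be consented and enrolled at the first study visit", section 10.1 says of that visit "Patients will be initiated on blinded study medication, as dictated by systolic blood pressure", and Appendix A marks "Dispense study medication" under Visit 1. The medication check listed for Visit 1 in section 10.1 is "Review of medications patient is actively taking, and the doses".

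Section 8.9 prohibits ACEIs while study treatment is under way. Section 9.6 says that sacubitril/valsartan is contraindicated with an ACEI or an ARB.

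On study drug interruption, section 10.2 says that "an attempt should be made to restart the study drug at the last tolerated dose when the subject is stable, per physician discretion". For a patient whose physician stops study drug and starts an ACEI, it adds "then a 36 hour wash-out period is required after the last dose of study drug before starting the ACEI".

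**The concern.** The protocol treats the switch from study drug to an ACEI as needing a timed gap. For the opposite switch, from an ACEI to study drug, it states no gap. The entry rule depends on whether the patient is currently on the drug, and that status can change on the day the ACEI is stopped.

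The patient left uncovered is one whose ACEI was discontinued shortly before Visit 1. On a literal reading this patient is no longer receiving the drug, passes exclusion 2, and may be given sacubitril/valsartan at a time when the protocol's own reasoning for the reverse switch would call for waiting. Because treatment is blinded, the investigator cannot limit caution to the active arm, so any rule has to cover everyone.

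The stake is the safety of individual patients. Prior ACEI use does not enter the sample size calculation in section 13.2 or the analysis in section 13.4.

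**Working it through.** The check is mainly textual: which sections could supply an interval from an ACEI to study drug, and does any of them do so?

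**1. Stated intervals**
- Study drug to ACEI: 36 hours (section 10.2).
- ACEI to first dose of study drug: none found.

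**2. Sections that might close the gap at entry**

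| Section | What it covers | Sets an interval before the first dose? |
|---|---|---|
| 7.3, exclusion 2 | Current ACEI treatment | No |
| 7.3, exclusion 6 | Earlier angioedema, allergy or intolerance | No |
| 7.3, exclusion 12 | Conditions that threaten compliance | No |
| 6.1 and 10.1, starting dose | Dose chosen by systolic pressure | No |
| 10.1, medication review | Drugs being taken now | No; does not ask when a stopped drug was last taken |
| 8.9 | ACEI use during the treatment period | No; does not reach back before it |
| 9.6 | Contraindication with an ACEI | No |

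**3. Who is left uncovered**
- A patient on a daily ACEI who took it yesterday and is continuing it is barred by exclusion 2.
- A patient who takes an ACEI after starting study drug breaches section 8.9.
- A patient whose ACEI was discontinued shortly before Visit 1 is not clearly caught by any rule.

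**4. Does the visit structure create a gap in practice?** Section 6.1 puts screening laboratory tests before randomisation. Patients in the imaging sub-study (about 30 of about 50) must also complete a baseline scan. Some hours may pass, but no minimum is set.

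**5. Cost of a hold, assuming 36 hours**
- Longest delay: 36 / 24 = 1.5 days.
- At entry, if randomisation itself is held, no doses are lost. The Visit 3 window of 77 to 91 days (84 ± 7) is unaffected, because follow-up starts later by the same amount.
- At a restart, if restarts after an ACEI are allowed: 36 / 12 = 3 twice-daily doses at most. Scheduled doses are 84 × 2 = 168, so the loss is 3 / 168 = 1.8%.

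No exposure or harm estimate is possible. The documents give neither the number of recent ACEI stoppers nor an event rate for overlap.

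**The case against.** The best defence is that the gap is nearly closed already. Current users are excluded, ACEIs are prohibited during treatment, patients with earlier angioedema or intolerance are removed, and medication is reviewed at Visit 1. What remains is a patient who stopped an ACEI within about a day and a half of dosing and whom the investigator judges to be off it. Nothing shows that such a patient is expected. This stands, and it is why the point is minor. It does not remove the point, because none of these safeguards sets a time.

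A second defence is that the documents do not establish the need for 36 hours in this direction. Section 9.6 speaks of use together, and section 10.2 gives no reason for its interval and does not call it symmetric. This also stands: the interval is borrowed and has to be labelled an assumption. Nor does the 96-hour fever rule show that a wash-out is needed, since it concerns symptoms. It shows only that a timed criterion fits the list.

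A reader might go further and infer that section 10.2 directs patients back onto study drug straight after an ACEI. The text does not settle this. The ACEI sentence can be read as permanent replacement of study drug, section 8.9 already rules out restarting while an ACEI continues, and a restart requires a stable patient and the physician's judgement. On the other hand, both sentences stand under the interruption heading, and the restart instruction covers stopping for any reason. The restart question is therefore a request to clarify intent, not a shown gap.

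**Conclusion.** The point holds as a minor design matter. The plan as written allows a patient who has just stopped an ACEI to be enrolled and dosed with no stated interval, although it calls the combination contraindicated and requires 36 hours in the other direction.

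The conclusion rests on two things: a literal reading of exclusion 2 as covering current treatment only, and the absence of an interval in every section checked. The number of affected patients is unknown, and no harm rate is claimed.

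Two stronger readings should be resisted. A reader might infer that daily ACEI users can slip into the trial; exclusion 2 ordinarily bars them, including a patient who took a dose the day before and is continuing. A reader might also infer that the trial's results are at risk; nothing in the endpoints, the analysis or the power calculation depends on this.

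**What to change.** 1. In sections 6.1 and 10.1, add a dosing rule for all participants: randomisation and the first dose of study drug are held until at least 36 hours after the last dose of any ACEI. A dosing rule is preferable to a longer exclusion criterion, because it delays the patient without making them ineligible and needs no re-screening provision.
2. At Visit 1, record the date and time of the last ACEI dose, including for drugs already stopped.
3. In section 10.2, state one of two things: that study drug is not restarted once an ACEI has been started, or that the same interval applies before any restart.
4. Before adopting 36 hours, check it against the prescribing information cited as reference 16.

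The cost is a short amendment and one extra recorded date and time. Any affected patient starts up to 1.5 days later. Holding randomisation, and not only the first dose, keeps the baseline biomarkers and the starting-dose blood pressure at the point where section 6.1 places them. If restarts after an ACEI are allowed, an affected patient misses at most 3 of 168 doses because of the hold.

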9.6 Summary of the Risks and Benefits

Blood draws: The risks of drawing blood include bleeding at the puncture site, bruising and pain. These occur in a very small portion of the population.

Cardiac Magnetic Resonance Imaging (sub-study patients only): Serious reactions to the contrast agent used during some MRI tests are very rare. However, side effects are possible and include headache, nausea, dizziness, changes in taste, and allergic reactions. Rarely, the contrast agent can harm people who have severe kidney or liver disease. The substance may cause nephrogenic systemic fibrosis.

Sacubitri/valsartan: Sacubitri/valsartan is indicated to reduce the risk of cardiovascular death and hospitalization for heart failure in adult patients with chronic heart failure.^{7, 8, 16} Moreover, sacubitri/valsartan has been shown to reduce mortality in patients with heart failure and reduced ejection fraction (HFrEF).⁷ This agent is recommended in all patients with HFrEF (Class I, Level of Evidence B-R), unless contraindicated.¹⁷

Sacubitri/valsartan is teratogenic and contraindicated in pregnancy. Use of drugs that act on the renin-angiotensin system (of which sacubitri/valsartan is included) during the second and third trimesters of pregnancy reduces fetal renal function and increases fetal and neonatal morbidity and death. When pregnancy is detected, discontinue study drug as soon as possible. These adverse outcomes are usually associated with use of these drugs in the second and third trimesters of pregnancy. There is no information regarding the presence of sacubitri/valsartan in human milk, the effects on the breastfed infant, or the effects on milk production. Sexually active subjects must agree to use appropriate contraception as long as they are taking study drug. Medically acceptable contraceptives include:

- surgical sterilization (such as a tubal ligation or hysterectomy)
- approved hormonal contraceptives (such as birth control pills, patches, implants or injections)
- barrier methods (such as a condom or diaphragm) used with a spermicide, or
- Intrauterine device (IUD)

Sacubitril/valsartan should be used with caution in the setting of concomitant non-steroidal anti-inflammatory drugs, lithium, other potassium-sparing diuretics. Sacubitril/valsartan is contraindicated with use an ACEI, ARB, and should not be used with aliskiren in patients with diabetes.

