In the PARADIGM-HF trial of patients with chronic heart failure with reduced ejection fraction, sacubitril/valsartan reduced the risk of cardiovascular mortality or heart failure hospitalization by 20%, as compared with guideline-indicated ACEI therapy (i.e., enalapril). In the PARADIGM-HF trial, use of sacubitril/valsartan was associated with a greater incidence of angioedema than the comparator drug enalapril (0.5% vs. 0.2%).⁷ The risk of angioedema with sacubitril/valsartan compared with enalapril was relatively greater among Black patients (2.4% vs. 0.5%). Patients with a history of angioedema are contraindicated from taking this drug. Trial data indicate adverse reactions occurring $\geq 5\%$ are hypotension, hyperkalemia, cough, dizziness, and renal failure. Symptomatic hypotension in PARADIGM-HF was more common among patients taking sacubitril/valsartan than enalapril (18% vs. 12%).⁷ In the PARAGON-HF trial, which tested the efficacy and safety of sacubitril/valsartan versus valsartan among patients with heart failure with preserved ejection fraction, no new adverse reactions were identified.⁸

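### The risk summary (9.6) calls any history of angioedema a contraindication, but exclusion 6 (7.3) bars only angioedema to ACEI, ARB or sacubitril/valsartan: a minor safety inconsistency to align

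*Combined protocol and SAP*

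**What the plan says.** Two places in the combined protocol and SAP deal with prior angioedema.

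- **Section 9.6, Summary of the Risks and Benefits:** "Patients with a history of angioedema are contraindicated from taking this drug". The sentence names no cause. It comes straight after two sentences giving angioedema incidence on sacubitril/valsartan and on enalapril in an earlier heart failure trial: 0.5% against 0.2% overall, and 2.4% against 0.5% in Black patients.
- **Section 7.3, Exclusion Criteria, item 6:** "Prior intolerance, allergy or angioedema to ACEI, ARB, or sacubitril/valsartan". Here the angioedema must have been a reaction to one of the named agents.

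Section 9.6 describes two other situations as contraindicated. On pregnancy it says "Sacubitri/valsartan is teratogenic and contraindicated in pregnancy". On combined use it says "Sacubitril/valsartan is contraindicated with use an ACEI, ARB, and should not be used with aliskiren in patients with diabetes". The corresponding exclusions are item 7, "Pregnant or breast-feeding", and item 2, "Actively receiving therapy with an angiotensin-converting enzyme inhibitor (ACEI), angiotensin II receptor blocker (ARB), aliskiren, or sacubitril/valsartan".

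Section 6.1 randomizes 1:1 those patients who have been confirmed to meet the eligibility criteria. Section 10.1 has medical history taken at Visit 1, and in section 16.1 the investigators undertake to follow the protocol.

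**The concern.** The group described in 9.6 is wider than the group removed by exclusion 6. The difference is patients with past angioedema of some other cause, or of a cause never established. If 9.6 means what it literally says, such a patient can satisfy every written criterion and have a one-in-two chance of receiving a drug that the same protocol says the patient should not take. Keeping that patient out would then rest on someone applying a sentence in the risk summary, because the criteria used to confirm eligibility do not require it.

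Exclusion 6 also works only through prior exposure. The criteria allow patients who have never taken an ACEI, an ARB or sacubitril/valsartan. They cannot have had angioedema to those drugs, so item 6 cannot pick up any earlier episode they had. The documents do not say how many enrolled patients would be in that position.

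What is at stake is the safety of individual patients at entry. The biomarker comparisons are not involved.

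**Working it through.** No arithmetic applies, and the plan gives no figure to reproduce. The check is whether the two texts differ and whether anything else in the document closes the gap.

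**Step 1: compare the three contraindications in 9.6 with the exclusion list.**

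| Stated as contraindicated in 9.6 | Item in 7.3 | Breadth of 7.3 relative to 9.6 |
|---|---|---|
| Pregnancy | 7 | Wider: adds breast-feeding |
| Use with an ACEI or ARB | 2 | Covers it, and bars aliskiren in everyone, where 9.6 advises against it only in diabetes |
| History of angioedema, no cause named | 6 | Narrower for angioedema: only when due to ACEI, ARB or sacubitril/valsartan |

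Two of the three are carried over at equal or greater breadth and one is not. Item 6 does add intolerance and allergy to the named drugs, but that does not reach angioedema of another cause.

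**Step 2: look for another criterion that catches the remaining patients.**

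- Section 7.2: none of the eight inclusion criteria mentions angioedema.
- Section 7.3, item 2: concerns current treatment, not history.
- Section 7.3, item 12: the only discretion clause. It is limited to conditions that threaten compliance with the protocol; safety and contraindications are not mentioned.
- Section 8.9: restricts concomitant drugs during treatment.
- Section 6.1 and Appendix A: refer to the eligibility criteria and add no separate check for contraindications.

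Angioedema appears only in 7.3 and 9.6, so none of these closes the gap.

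**Step 3: look for a safeguard after randomization.** No later section names angioedema as a reason to stop the drug for good. Section 10.2 asks for an attempt to restart after any interruption once the patient is stable, at the physician's discretion. That discretion is real protection, but it operates only after exposure. The entry criteria remain the main written screen for prior angioedema.

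**Step 4: can the problem be sized?** That would need the proportion of candidates with past angioedema from other causes, and their risk on the drug. The documents give neither. The percentages in 9.6 are incidences in treated heart failure patients and cannot stand in for either quantity. All that can be said is that very few, if any, of about 50 patients would be concerned.

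**The case against.** The strongest reply is that 9.6 is a loosely worded summary and exclusion 6 is the operative text. The contraindication sentence directly follows a comparison of angioedema on two drugs, so drug-related angioedema may be all that was meant. On that view, the care with which pregnancy and ACEI/ARB use were turned into exclusions suggests that the authors also wrote item 6 precisely, and the fault, if any, is an over-broad sentence in 9.6. This is a fair reading and the documents cannot rule it out. The prescribing information that would decide it is cited but not reproduced. Against it, 9.6 does state a limit where it wants one, as with aliskiren and diabetes, and it states none for angioedema. The question therefore stays open, and on either reading one of the two texts needs correcting.

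A second reply is that the gap is partly covered in practice. Section 9.6 is itself protocol text that the investigators agree to follow, medical history is taken at Visit 1, and this is a single centre. The eligibility case report form is not among the documents, so it may already ask about angioedema. All of this stands. It makes a wrong entry less likely, but the criteria still do not require the exclusion.

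A reader might go further and infer that the eligibility list is established to be wrong, or that the plan knowingly admits contraindicated patients. The documents do not support that: they show two wordings that disagree, not which is correct. A reader might also apply the 0.5% or 2.4% figures to the patients left uncovered. Those figures do not describe people with earlier angioedema of another cause, and the most direct drug-related histories are already excluded.

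**Conclusion.** The inconsistency is real as a matter of wording: 9.6 names no cause, exclusion 6 does, and no other criterion covers the difference. Which text reflects the intention cannot be settled from the documents. The point is minor. It bears on the safety of very few, if any, of about 50 patients, has no measurable size, and does not affect the endpoints, the power calculation or the analysis.

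That the texts disagree rests on no assumption beyond reading both as written. That a contraindicated patient could be randomized holds only if 9.6 is meant literally and the investigator does not act on it independently. The point is still worth correcting before enrolment, because the remedy is small and the consequence would fall on a patient.

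**What to change.** As the safe default, reword exclusion 6 in section 7.3 to: *History of angioedema of any cause, or prior intolerance or allergy to ACEI, ARB, or sacubitril/valsartan.* Make sure the eligibility case report form carries a matching item.

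If the sponsor confirms from the prescribing information that only drug-related angioedema is contraindicated, leave exclusion 6 as it is and limit the sentence in 9.6 to the same causes.

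The first option costs a one-line amendment, at most one form item, and the loss of very few, if any, of about 50 patients. If 9.6 meant only drug-related angioedema, that small loss is its only downside. The second option costs a one-line edit to 9.6 and leaves eligibility unchanged. Neither requires any change to the sample size or the analysis.
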